1. STUDY OBJECTIVES

1.1 Primary Mechanistic and Relevant Clinical Objectives

Primary Mechanistic Objective: To determine the effect of active, inhibitory rTMS (continuous theta-burst stimulation-cTBS) over left dorsolateral prefrontal cortex (L-DLPFC) on modulating the neural network that underlies hypnotizability and hypnosis. **In other words, the Primary Outcome Measure** is the change in functional connectivity between the L-DLPFC and the dACC in active versus sham rTMS and the effect of rTMS inhibition of activity in the DLPFC on activity in the dACC.

Primary Mechanistic Hypothesis: Active, inhibitory rTMS (cTBS) over L-DLPFC will modulate the neural network that underlies hypnotizability by producing greater increases in functional connectivity between L-DLPFC and dACC as compared to sham rTMS (sham cTBS). We hypothesize that active, inhibitory rTMS (continuous theta-burst stimulation) will produce increases in functional connectivity between the L-DLPFC and the dACC, producing a transient phenotype appearing on neuroimaging like a high hypnotizable. This increase in functional connectivity, coupled with inhibition of *activity* in the DLPFC, would be hypothesized to reduce activity in the dACC as well, which is what we have shown to be associated with entry into the hypnotic state. Thus rTMS-induced increase in functional connectivity should increase hypnotizability and, coupled with inhibited activity, enhance hypnotic intensity as well.

Relevant Clinical Objective: To determine the effect of active, inhibitory rTMS (cTBS) over L-DLPFC on enhancing the efficacy of hypnotic analgesia (HA) as measured by change in pain thresholds.

Relevant Clinical Hypothesis: Active, inhibitory rTMS (cTBS) over L-DLPFC will enhance the efficacy of hypnotic analgesia (HA) as compared to sham rTMS (sham cTBS).

1.2 Secondary Objectives

Secondary Objective A: *To determine the effect of active, inhibitory rTMS (cTBS) over L-DLPFC on modulating the neural network that underlies hypnotic intensity.*

Secondary Hypothesis A: *Active, inhibitory rTMS (cTBS) over L-DLPFC will modulate the neural network that underlies hypnotic intensity by decreasing activity in L-DLPFC and dACC as compared to sham rTMS (sham cTBS) as measured by BOLD fMRI and interleaved TMS-MRI.*

Secondary Objective B: *To determine the effect of active, inhibitory rTMS (cTBS) over L-DLPFC on enhancing hypnotizability (as measured by the Hypnotic Induction Profile-HIP and Stroop Task) and hypnotic intensity (as measured by the Hypnotic Intensity Scale-HIS).*

Secondary Hypothesis B: *Active, inhibitory rTMS (cTBS) over L-DLPFC will increase the HIP and HIS scores as well as hypnotic reduction of the Stroop Effect as compared to sham rTMS (sham cTBS).*

Secondary Objective C: *To determine the effect of active, inhibitory rTMS (cTBS) over L-DLPFC on the neural network underlying the conflict regulation system as a surrogate of effective modulation of the neural circuitry that underlies hypnotizability.*

Secondary Hypothesis C: *Active, inhibitory rTMS (cTBS) over L-DLPFC will modulate the neural network that underlies conflict regulation by producing greater increases in functional connectivity between the right inferior frontal gyrus (rIFG) and the default mode network (DMN) as compared to sham rTMS (sham cTBS).*

Secondary Objective D: *To determine the effect of active, inhibitory rTMS (cTBS) over L-DLPFC on the neural network that underlies the post-hypnotic Stroop Effect.*

Secondary Hypothesis D: *Post-hypnotic instruction of word blindness after active, inhibitory rTMS (cTBS) over L-DLPFC will reduce dACC activity during the Stroop task (similar to high hypnotizables) as compared to sham rTMS (sham cTBS).*

Secondary Objective E: *To determine the effect of active, inhibitory rTMS (cTBS) over L-DLPFC on modulating the neural network that underlies hypnotic analgesia (HA).*

Secondary Hypothesis E: *Active, inhibitory rTMS (cTBS) over L-DLPFC will modulate the neural network that underlies HA by producing a decrease in activity and an increase functional connectivity among the anterior cingulate, dorsolateral, insular, and somatosensory cortices (hypnotic analgesia network) as compared to sham rTMS (sham cTBS).*

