- Spectroscopy: Non-invasive magnetic resonance spectroscopy (MRS) will be used to quantitatively measure brain metabolites, including both inhibitory and excitatory neurotransmitters as well as markers of inflammation.

Pre-rTMS Stroop Assessment

Hypnotic Stroop and Non-Hypnotic Stroop Pre-rTMS Scan Session: This session includes all of the pre-rTMS questionnaires, behavioral evaluations and scans necessary to compare to the post-rTMS.

- Medication Washout, Drug Screen, Pregnancy Test Form: This form will be administered at the beginning of each pre-rTMS assessment to ensure medication washout compliancy (if applicable), document drug screen results, and screen for pregnancy (if applicable).
- Hypnotic Induction Profile: This administration of the HIP will serve as the baseline measure for comparison after the rTMS stimulation session(87). HIP will be measured on three separate occasions throughout the stroop assessment visit - 1) immediately following the pre-rTMS stroop MRI session, 2) immediately following rTMS, and, 3) immediately following the post-rTMS stroop MRI session.
- Stroop Task: This administration of the Stroop task will serve as the baseline measure for comparison to the post-rTMS session(32, 118).
- Pre-TMS Hypnotizability Scan Session (1 hour duration)
 - Structural Acquisition (T1): This structural scan is necessary for several reasons: demonstration that the participant's brain is structurally normal, imaging analysis, and rTMS targeting(81).
 - BOLD fMRI Acquisitions
 - Resting State: This is the baseline scan required for the primary endpoint. Individuals with high hypnotizability have been demonstrated to have higher functional connectivity between the dorsolateral prefrontal cortex and the dorsal anterior cingulate cortex (31).
 - Stroop Task: Brain activity while performing conflict tasks has been demonstrated to be different depending on a subject's level of hypnotizability. This baseline would demonstrate the subject's normal functional brain response to the Stroop Task

(32). Functional brain response to the stroop task will be measured following hypnosis (Hypnotic Stroop) and non-hypnosis (Non-Hypnotic Stroop) audio instructions. These acquisitions will be randomized to prevent order effects. Highly hypnotizable individuals can have a loss of the Stroop Effect with specific post-hypnotic instruction (119, 120) which correlates with the reduction in neural activity during conflict (35).

Pre-rTMS Analgesia Assessment

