6.2.5 Post-rTMS (Active and Sham) Evaluations

Post-rTMS Stroop Assessment

Hypnotic Stroop and Non-Hypnotic Stroop Pre-rTMS Scan Session: This session includes all of the post-rTMS behavioral evaluations and scans necessary to compare to the pre-rTMS.

- Hypnotic Induction Profile: This administration of the HIP will serve as the post-rTMS measure for comparison to the pre-rTMS stimulation session.
- Post-TMS Hypnotizability Scan Session (1 hour duration)
 - Structural Acquisition (T1): This structural scan is necessary for several reasons: demonstration that the participant's brain is structurally normal, imaging analysis, and rTMS targeting(81).
 - BOLD fMRI Acquisitions
 - Resting State: This is the scan required for evaluation of the primary endpoint. Individuals with high hypnotizability have been demonstrated to have higher functional connectivity between the dorsolateral prefrontal cortex and the dorsal anterior cingulate cortex (31).
 - Stroop Task: Brain activity while performing conflict tasks has been demonstrated to be different depending on a subject's level of hypnotizability. These scans will demonstrate the subject's functional brain response to the Stroop Task post-rTMS. Functional brain response to the stroop task will be measured following hypnosis (Hypnotic Stroop) and non-hypnosis (Non-Hypnotic Stroop) audio instructions. Randomization of hypnosis and non-hypnosis scan order for each participant will be kept consistent between both pre- and post-rTMS scans. Highly hypnotizable individuals can have a loss of the Stroop Effect with specific post-hypnoitic instruction (119, 120) which correlates with the reduction in neural activity

during conflict (35).

Post-rTMS Analgesia Assessment

Post-rTMS Analgesia Session: This hour-long scan session includes all of the post-rTMS behavioral evaluations and scans necessary to compare to the pre-rTMS.

- Hypnotic Induction Profile: This administration of the HIP will serve as the baseline measure for comparison after the rTMS stimulation session(87).
- Pre-TMS Scans
 - Structural Acquisition (T1): This structural scan is necessary for several reasons: demonstration that the participant's brain is structurally normal, imaging analysis, and rTMS targeting (81).
 - BOLD fMRI Acquisitions

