Validity of the Approach: It has been previously demonstrated that inhibitory rTMS over the L-DLPFC can modulate the level of hypnotizability of the subject (26). Because rTMS has been demonstrated to affect hypnotizability and it is suspected that rTMS (26) will therefore affect hypnotic intensity (133). It has been demonstrated that rTMS can manipulate the Stroop effect bi-directionally, in a frequency-dependent manner (118, 153, 154). It has also been demonstrated that performance on conflict tasks such as the Stroop task and the flanker task are correlated with hypnotizability (32).

Reliability of the Approach: It has been demonstrated across numerous studies that rTMS is capable of modulating cognitive tasks in a frequency-dependent manner (155-157).

Secondary Objective C: To determine the effect of active, inhibitory rTMS (cTBS) over L-DLPFC on the neural network underlying the conflict regulation system as a reflection of effective modulation of the neural circuitry underlying hypnotizability.

Secondary Hypothesis C: Active, inhibitory rTMS (cTBS) over L-DLPFC will modulate the neural network that underlies conflict regulation system by decreasing activity in right inferior frontal gyrus (rIFG) and the connectivity of the rIFG to the default mode network (DMN).

Validity of the Approach: Difference in hypnotizability has been correlated with difference in neural strategy for conflict tasks such as the Stroop task and the flanker task (32).

Reliability of the Approach: It has been demonstrated that both the BOLD and functional connectivity measures are reliable across numerous studies (51).

Secondary Objective D: To determine the effect of active, inhibitory rTMS (cTBS) over L-DLPFC on the neural network underlying post-hypnotic Stroop Effect.

Secondary Hypothesis D: Post-hypnotic instruction of word blindness after active, inhibitory rTMS (cTBS) over L-DLPFC will reduce dACC activity during the Stroop task (similar to high hypnotizables) as compared to sham rTMS (sham cTBS).

Validity of the Approach: It has been demonstrated that a post-hypnotic instruction of word blindness will produce a loss of the Stroop Effect in highly hypnotizable individuals (119, 120). It has also been demonstrated that the loss of the Stroop Effect is correlated with reduction in conflict signaling in the dorsal anterior cingulate (35).

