For each run, a first-level general linear model (GLM) will be conducted using FMRIB's improved linear model prewhitening convolved using a boxcar regressor model (101). Across runs and for each contrast, a within-subject fixed effects analysis will be performed. For group analysis, FMRIB's local analysis of mixed effects will be used within a mask of our a priori ROIs dACC and L-DLPFC, thresholded using family-wise error (FWE) corrected $Z > 2.3$; cluster $p < 0.05$. Average contrast of parameter estimate values will be extracted from our ROIs and Spearman's correlations will be calculated between these values and differences in active versus sham rTMS.

Primary Mechanistic Hypothesis: *Active, inhibitory rTMS (cTBS) over L-DLPFC will modulate the neural network that underlies hypnotizability by producing greater increases in functional connectivity between DLPFC and dACC and reduced activity in both L-DLPFC and dACC.*

Connectivity between L-DLPFC and dACC will be assessed with resting state functional connectivity MRI (31, 51) at the baseline time-point and as well as at the post-rTMS time-point for both rTMS conditions (active and sham). It is hypothesized that inhibitory rTMS (cTBS) to DLPFC will result in increased fc between the DLPFC and dACC. Analyses will be restricted to the dACC and L-DLPFC for the Primary Outcome Measure. To determine if the active rTMS condition is specifically associated with change in dACC and DLPFC functional connectivity, a mask restricted to dACC and DLPFC will be utilized to extract the fMRI connectivity data. It is expected that the correlation in active rTMS group over L-DLPFC to be stronger than the correlation obtained in the sham rTMS group. Regression analysis will be used to investigate whether greater connectivity will be present between L-DLPFC and dACC for active versus sham rTMS (cTBS). Activity in both regions will be measured using the fractional amplitude of low-frequency fluctuation (fALFF) of the fMRI signal to measure the amplitude of regional spontaneous activity throughout the brain. (164) It is a ratio of the power spectrum of low-frequency (0.01-0.08 Hz) to that of the entire frequency range, thereby controlling for overall physiological noise.

Relevant Clinical Outcome: *To determine the effect of active, inhibitory rTMS over DLPFC on enhancing hypnotic analgesia.*

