Hypnosis Scans for Secondary Outcome Measure D: All participants will receive the same identical pre-rTMS post-hypnotic suggestion Stroop task scan(35). After randomization (to either active DLPFC rTMS or sham rTMS) where one half (n=45) will receive active DLPFC rTMS (cTBS), and one-half sham DLPFC rTMS (cTBS) (n=45)(30), all participants have their post-rTMS post-hypnotic suggestion Stroop task scan session(35).

fMRI Preprocessing and Analysis: All fMRI data will be preprocessed and analyzed using FSL (FMRIB Software Library, version 5.0) and in the manner described in the Primary Outcome Measure. For group analysis, FMRIB's local analysis of mixed effects will be used within a mask of our a priori ROIs ACC and DLPFC, thresholded using family-wise error (FWE) corrected $Z > 2.3$; cluster $p < 0.05$. Average contrast of parameter estimate values will be extracted from the ROIs and Spearman's correlations will be calculated between these values and differences in active versus sham rTMS.

Secondary Hypothesis D: Post-hypnotic instruction of word blindness after active, inhibitory rTMS (cTBS) over L-DLPFC will reduce dACC activity during the Stroop task (similar to high hypnotizables) as compared to sham rTMS (sham cTBS).

Activity in dACC will be assessed with fMRI(35) at the baseline time-point and as well as at the post-rTMS time-point for both rTMS conditions (active and sham). Long-lasting (~1 hour) inhibitory rTMS (spaced continuous theta-burst stimulation approach(30)) will be applied to L-DLPFC and expect that the stimulation-induced functional connectivity between these two nodes would be increased as a surrogate of increased hypnotizability and therefore increased post-hypnotic Stroop Effect.

Analyses will be restricted to the dACC and DLPFC for this Secondary Outcome Measure. To determine if rTMS condition during the hypnotic state is specifically associated with change in dACC and DLPFC activity, a mask restricted to dACC and DLPFC will be utilized to extract the fMRI activity. The correlation in active rTMS group over L-DLPFC is expected to be stronger than the correlation obtained in the sham rTMS group. Regression analysis will determine the strength of the relationship between the reductions of fMRI activity between dACC and L-DLPFC with active versus sham rTMS conditions.

Secondary Outcome E: *To determine the effect of active, inhibitory rTMS over DLPFC on modulating the neural network that underlies hypnotic analgesia.*

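### Secondary D tests dACC activity only in the Stroop run after the post-hypnotic suggestion, so it estimates the total cTBS effect under suggestion but cannot show that the effect is specific to the suggestion

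*Combined protocol and SAP*

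**What the plan says.** **Hypothesis and test.** Protocol 1.2 words Secondary Hypothesis D as "Post-hypnotic instruction of word blindness after active, inhibitory rTMS (cTBS) over L-DLPFC will reduce dACC activity during the Stroop task", likening this to high hypnotizables and taking sham as comparator. The scan named for D in 9.6.2 is the suggestion run: "All participants will receive the same identical pre-rTMS post-hypnotic suggestion Stroop task scan(35" (the trailing number is a citation), repeated after rTMS. The regression described there is by stimulation arm. Section 9.7 applies the same baseline-to-post, active-versus-sham strategy to D. No section defines a hypnotic-minus-non-hypnotic contrast or a suggestion-by-arm term for D.

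**Prediction for cTBS in general.** Section 1.1 says that increased connectivity together with inhibited DLPFC activity "would be hypothesized to reduce activity in the dACC as well". Section 9.6.1 puts this into the primary hypothesis, as "producing greater increases in functional connectivity between DLPFC and dACC and reduced activity in both L-DLPFC and dACC", and specifies the measure: "Activity in both regions will be measured using the fractional amplitude of low-frequency fluctuation (fALFF) of the fMRI signal". This stands beside resting-state connectivity and involves no suggestion.

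**The other Stroop run.** Section 6.2.2: "Functional brain response to the stroop task will be measured following hypnosis (Hypnotic Stroop) and non-hypnosis (Non-Hypnotic Stroop) audio instructions". Section 6.2.5 repeats both runs after stimulation and adds: "Randomization of hypnosis and non-hypnosis scan order for each participant will be kept consistent between both pre- and post-rTMS scans".

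**Separate SAP (January 2024).** It covers the HIP scores and the test of the blind, and adds nothing on D.

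**The concern.** Hypothesis D makes the post-hypnotic instruction the agent of the reduction, and 9.6.2 links the expected change to greater hypnotizability and hence a stronger post-hypnotic Stroop effect. Two accounts predict the same result in the planned comparison:

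- cTBS makes participants respond more to the word-blindness suggestion.
- cTBS lowers dACC activity whether or not a suggestion is given.

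Only the first is specific to the suggestion. The suggestion run cannot tell them apart; a Stroop run without the suggestion can, and the trial acquires one. What is at stake is the mechanistic reading of a positive D, in a trial whose purpose is mechanistic.

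**Working it through.** **1. Stated figures.** The documents give no sample size, power or effect size for D, so there is nothing to reproduce. Section 9.2 says that for D effect sizes and p-values will be monitored, with more weight on effect sizes.

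**2. What each comparison estimates.** Let g be a general cTBS effect on the pre-to-post change in Stroop dACC response, common to both runs. Let s be the additional effect present only after the suggestion. For active minus sham:

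| Quantity compared | Expected difference |
|---|---|
| Change in Hypnotic run (planned D) | g + s |
| Change in Non-Hypnotic run | g |
| Change in (Hypnotic minus Non-Hypnotic) | s |

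The planned comparison is unbiased for g + s, since both arms receive the suggestion before and after stimulation. It carries no information on how the sum divides.

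**3. Inputs for the illustration.** From 9.2: 40 usable participants per arm and two-sided alpha 0.05. Assumed: SD of each run's change score 1; g of 0.3, 0.5 or 0.8 SD, equal in both runs; s = 0; correlation rho between the two runs' change scores 0.3 to 0.7. The 0.8 is also the value that 9.2 adopts, but for the primary connectivity outcome.

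**4. Planned test when s = 0.** Two-sample t, df = 2 × 40 − 2 = 78, critical value 1.991, noncentrality = g × sqrt(40/2).

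| g (SD) | Noncentrality | P(significant) |
|---|---|---|
| 0.3 | 1.342 | 0.263 |
| 0.5 | 2.236 | 0.598 |
| 0.8 | 3.578 | 0.942 |

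**5. Between-run contrast when s = 0.** The common effect g cancels within each participant, so the rejection rate is the nominal 0.05. Simulation (20,000 trials per setting, common effects of 0.42 and 0.8 SD, rho 0.3, 0.5 and 0.7) gave 4.8% to 5.1%.

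**6. Precision of the contrast.** Its standard error relative to the single-run change is sqrt(2(1 − rho)). The last column is power for s = 0.8 SD.

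| rho | SE ratio | Power |
|---|---|---|
| 0.3 | 1.18 | 0.848 |
| 0.5 | 1.00 | 0.942 |
| 0.7 | 0.77 | 0.995 |

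The contrast is noisier than the planned test only if rho is below 0.5.

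**7. Does Secondary C fill the gap?** Section 9.7 lists the conflict task (C) separately from the post-hypnotic conflict task (D). However, C's regions of interest in 9.6.2 are rIFG, default-mode nodes and attentional nodes, without dACC. One sentence under C does mention dACC and L-DLPFC activity by arm, but no comparison of C with D is planned.

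**The case against.** **The planned comparison answers the stated objective.** Objective D asks for the effect of cTBS on the network underlying the post-hypnotic Stroop effect, stimulation is the randomised factor, and the comparator is sham. This stands. A reader might infer that D cannot answer its own objective; the documents do not support that. The limit is on calling the effect suggestion-specific.

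**A general dACC reduction may be part of the intended phenotype.** Section 1.1 ties it to entry into the hypnotic state, and 2.2 reports less dACC activity in highs than lows during a flanker task. Subtracting the Non-Hypnotic run would remove that part. This also stands, and is why the contrast should sit beside the planned comparison rather than replace it.

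**The general prediction is clearest at rest.** In 9.6.1 activity is resting fALFF, not Stroop-evoked BOLD. Sections 1.1 and 9.1 state the reduction generally, but its carry-over to the Stroop task is an inference.

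**The percentages are not false-positive rates.** A reader might take 26% to 94% as type I error. D's stated null is that active equals sham, and with a real cTBS effect rejecting it is correct. The figures are power to detect that effect under assumed sizes.

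**Masking is not shown.** Section 9.1 says "It has been demonstrated that rTMS can manipulate the Stroop effect bi-directionally, in a frequency-dependent manner", from which a reader might infer that a direct effect could equally hide a real suggestion effect. That sentence supports Secondary B, concerns the Stroop effect rather than dACC activity, and makes direction depend on frequency. This trial uses one inhibitory regimen, for which the protocol predicts a decrease in dACC activity.

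**The added contrast has its own weakness.** Run order is randomised, so some participants take the Non-Hypnotic run after the word-blindness suggestion, which may carry over. The order term in 9.7 concerns scan-session days, not runs. This stands and shapes the fix.

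**Conclusion.** The point holds as a limit on interpretation. D as planned yields a valid total cTBS effect on dACC activity under suggestion. It does not separate a suggestion-specific effect from the general reduction that the protocol also expects, although the run that could do so is collected before and after stimulation. If the whole effect were general and of 0.3 to 0.8 SD, D would be significant in about 26% to 94% of trials of this size with nothing specific to the suggestion. That range rests on the assumed effect sizes, equal effects in both runs, and 40 usable per arm. The structural conclusion does not depend on those values. D is a secondary outcome with emphasis on effect sizes, so the consequence is for mechanistic attribution, not for the primary result.

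**What to change.** In 9.6.2 (Secondary D) and 9.7:

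1. Keep the hypnosis-run comparison and describe it as the total effect of cTBS on dACC activity under suggestion.
2. Add, per participant, the pre-to-post change in (Hypnotic minus Non-Hypnotic Stroop) dACC response. Compare arms with the 9.2 linear model plus a term for run order (hypnosis first or second).
3. Report the Non-Hypnotic change by arm beside it.
4. Show the contrast by run order as well, because carry-over may affect those who take the Non-Hypnotic run second.
5. Call an effect suggestion-specific only if the contrast supports it.

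The SAP reports analyses in the past tense. If the data are already unblinded, label the contrast post hoc.

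The cost is wording and one further model, with no new scans or visits. The downsides are lower precision if the runs' change scores correlate below 0.5, and possible carry-over, which the order term and the split by order expose but do not remove.
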